Demographic and phenotypic data will be collected at this time. Patients will be asked to report demographic information including age, sex, ethnicity, education level, income level, and marital status. In addition, patients will be administered an enrollment survey which will collect domains important to the pain experience. These are listed in table 2. All patient information will be recorded by a trained research assistant or the patient via direct entry. We will assess treatment expectation using a modified survey that uses Likert scales prior randomization. In addition, we will administer weekly surveys of pain severity and to assess whether adverse events are experienced weekly through 6 weeks (these brief surveys will be sent at 2 weeks, 4 weeks and 5 weeks). Adverse events will also be monitored at 3 weeks, 6 weeks, and 3 months following administration of study drug.

Table 2. Assessments by domain at each timepoint

Domain	Measure	D1	3W	6W	3M
Demographic information	Age, sex, gender, race/ethnicity, education, income, marital status	●			
Pre-MVC	Pain catastrophizing scale ²⁶ , PROMIS Item Bank v1.0 - Emotional Distress – Anxiety ²⁷ , PROMIS Item Bank v1.0 - Emotional Distress - Depression ²⁷ , Anxiety Sensitivity Index ⁵¹	●	●	●	●
Traumatic Event	Details of Traumatic Event, Concussion, Traumatic Brain Injury, Life events checklist ²⁸	●			
MVC Injury Severity	Abbreviated injury scale ²⁹	●			
Pain	Numeric Rating Scale, [†] RPS ³⁰ , PROMIS Short Form v1.0 - Pain Interference 4a ³¹ , PROMIS Scale v2.0 - Neuropathic Pain Quality 5a ³² , PROMIS Scale v2.0-Nociceptive Pain Quality 5a	●	●	●	●
Somatic Symptoms	Pennebaker Inventory of Limbic Languidness ⁵²	●	●	●	●
Global Mental and Physical Health	PROMIS Scale v1.2 - Global Mental 2a ³³ , PROMIS Scale v1.2 - Global Physical 2a ^{33,34}	●	●	●	●

Anxiety/Depressive Symptoms	PROMIS Item Bank v1.0 - Emotional Distress – Anxiety ²⁷ , PROMIS Item Bank v1.0 - Emotional Distress - Depression ²⁷	●	●	●	●
Posttraumatic stress symptoms	PTSD Symptom Severity index-interview for DSM-5 ³⁵ , Peritraumatic Distress Inventory items (PDI) ⁵³	●	●	●	●
Dissociative Symptoms	Michigan Critical Events Perception Scale ³⁶	●			
Analgesic Medication Use	Daily milligram morphine equivalents, non-opioid analgesic use, Date of opioid cessation (first day in three consecutive where patient took no opioids) ³⁷ .	●	●	●	●
Substance abuse	PROMIS Short Form v1.0 - Severity of Substance Use (Past 30 days) 7a ³⁸	●	●	●	●

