5.4 Text messaged or e-mailed outpatient Weekly Pain and Compliance Assessments

Brief, weekly assessments of pain severity (0-10 NRS), and review of any AEs over the past week will occur via e-mailed surveys administered through our secure study database REDCap. Patients will receive text messages from the Data Coordinating Center based on a predetermined schedule based on progress, using the secure study phone number. If

patients are not able to respond via text messaging or e-mail, they will be called by investigative team. This brief survey will be administered at 2 weeks, 4 weeks, and 5 weeks.

5.5 3- and 6-week assessment

The goal of this assessment is to perform a comprehensive phenotypic follow-up and a questionnaire assessing domains listed in table 2 will be assessed. Outcome assessments will be performed via structured survey either via a web-based Redcap survey emailed to their on-file email address or via telephone. Multiple methods of contacting participants are involved to best meet the needs of each individual participant. Patients will receive automated REDCap email reminders. Participants will also receive text reminders based on a predetermined schedule based on progress. If patients are not able to respond via text messaging or e-mail, they will be called by investigative team.

5.6 3-month assessment

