Similar models as for the primary outcome will be fit for both the Brief Pain Inventory and the SF-12 Mental and Physical Component Scale Scores.

Sex as a biological variable (SABV) will be examined in treatment response including sex-by treatment interaction terms in the mixed effect model specified above and exploring sex differences in therapeutic response to Vitamin D and n-3 PUFAs.

General mental and physical health will be assessed using SF-12 physical and mental component scores (PCS and MCS) and the impact on physical and mental functioning will be determined in each of the treatment groups. A clinically important reduction in SF-12 PCS and MCS ranges between 2.5-4.5⁵⁰; therefore, a reduction of ≥ 4.5 will be considered a clinically significant improvement MCS/PCS.

Brief Pain Inventory: We will also use multivariable analysis to determine the role of n-3 PUFA/Vitamin D supplementation in pain interference using composite and individual measures of the Brief Pain Inventory.

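### Section 6.1 plans secondary models on the Brief Pain Inventory and SF-12, which Table 2 never schedules, while the PROMIS scales collected for the same domains have no stated analysis

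*Combined protocol and SAP*

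**What the plan says.** Under Secondary Analyses, section 6.1 makes four relevant statements.

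- Models similar to the primary mixed model "will be fit for both the Brief Pain Inventory and the SF-12 Mental and Physical Component Scale Scores". A later paragraph adds a multivariable analysis of pain interference, based on the Brief Pain Inventory both as a composite and by its separate measures.
- General mental and physical health is to be measured by the SF-12 component scores. The plan gives 2.5 to 4.5 points as the range of a clinically important reduction, and concludes that a reduction of at least 4.5 "will be considered a clinically significant improvement MCS/PCS".
- Sex differences are to be studied through a sex-by-treatment term in the primary model, and by "exploring sex differences in therapeutic response to Vitamin D and n-3 PUFAs".
- The pain-interference paragraph again pairs n-3 PUFA with Vitamin D as the supplementation under study.

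Table 2 in section 5.1 is the assessment schedule. Its pain row includes "PROMIS Short Form v1.0 - Pain Interference 4a", and its global health row lists "PROMIS Scale v1.2 - Global Mental 2a" with the matching physical scale. Both rows are marked at day 1, 3 weeks, 6 weeks and 3 months. For the follow-up visits, sections 5.5 and 5.6 say that "a questionnaire assessing domains listed in table 2 will be assessed".

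**The concern.** An analysis plan can only be carried out on outcomes that the schedule collects. Here the two instruments that section 6.1 names for pain interference and general health are not in the schedule, and the instruments that are in the schedule for those domains have no analysis. Someone will have to decide later which collected scales take the place of the named ones. Table 2 holds many patient-reported scales, so a choice made after results are visible would leave room for selective reporting. The pilot is meant to inform a larger trial (sections 1 and 2.3), so it matters that its secondary outcomes are fixed in advance.

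Two further faults sit in the same text. A responder rule that counts a fall in a health score as a gain would misclassify participants if anyone applied it. A treatment that is not in the trial cannot have its effect estimated.

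**Working it through.** No sample size, power or alpha figure depends on this point, and the one number involved, 4.5, comes from a cited source and cannot be recalculated from the documents. The check is a comparison of the analysis text with the schedule and the arms.

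**Step 1: instruments.**

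| Domain | Named in 6.1 | Times scheduled in Table 2 | Collected instead | Times scheduled | Analysis stated in 6.1 |
|---|---|---|---|---|---|
| Pain interference | Brief Pain Inventory | 0 of 4 | PROMIS Pain Interference 4a | 4 of 4 | None |
| Mental health | SF-12 MCS | 0 of 4 | PROMIS Global Mental 2a | 4 of 4 | None |
| Physical health | SF-12 PCS | 0 of 4 | PROMIS Global Physical 2a | 4 of 4 | None |

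Both instruments named in 6.1 are absent. Three collected scales at four times each, 3 × 4 = 12 scheduled measurements per participant, have no stated analysis.

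**Step 2: could another visit supply them?** The 3-week, 6-week and 3-month questionnaires are defined by Table 2 (sections 5.5 and 5.6). The brief surveys at 2, 4 and 5 weeks hold only the 0-10 pain score and adverse events (section 5.4). Apart from section 6.1, the SF-12 and its component scores appear only in the abbreviation list, and the Brief Pain Inventory appears nowhere else.

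**Step 3: does another text name the secondary outcomes?** Section 2.2 refers to secondary outcomes without naming an instrument. Section 3.4 ends with the words of a secondary-endpoint heading and nothing under it in the text available. Neither resolves the mismatch.

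**Step 4: direction of the 4.5-point rule.** Section 6.1 presents the component scores as measures of general mental and physical health, but does not say which direction is better.

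- If a higher score means better health (an assumption, but the natural reading of a health score), a participant who falls by 4.5 counts as improved, and one who gains 4.5 does not.
- If a lower score means better health, the rule is the right way round. Nothing in the documents says this.

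**Step 5: treatments.** Sections 3.2 and 4.3 describe two groups, ergocalciferol and placebo, allocated 1:1. N-3 PUFA is neither of the two, and is mentioned only in the two places in section 6.1.

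**Step 6: what still works.** The sex-by-treatment term belongs to the primary model, whose outcome is the 0-10 pain score, and that score is collected. On the same outcome, the section 2.2 analyses by race, sex and initial vitamin D level, and with adjustment for baseline psychosocial differences, can be run. So can the analgesic-use analysis in section 4.6, because medication use is in Table 2. Only where section 2.2 extends the stratified analyses to secondary outcomes does it inherit the gap.

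**The case against.** The strongest reply is that the damage is narrow. The unmatched instruments have obvious counterparts in Table 2, so an analyst would probably settle on the right ones. The n-3 PUFA wording looks like a leftover, and striking it leaves the Vitamin D sex analysis intact. The 4.5-point rule feeds no test or decision, and the planned mixed model of scores does not depend on it. Section 6.1 also has models developed on dummy treatment assignments before unblinding, which limits data-driven choices.

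Most of this stands, and it rules out three stronger readings that a reader might infer.

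- That the secondary analyses as a whole cannot be run: those on the pain score and on analgesic use can be.
- That every secondary efficacy outcome is unobtainable: section 6.1 does not present these two instruments as the full set, and the bare heading in section 3.4 may be a gap in the extracted text.
- That the responder rule would reverse the trial's conclusion: no conclusion rests on it, and the instrument it applies to is not scheduled.

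What does not stand is the appeal to the blind review. Its stated purpose is to settle model covariates, and it does not fix which instruments serve as outcomes. An obvious counterpart is still not a prespecified one.

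**Conclusion.** The point holds for two planned analyses. The Brief Pain Inventory and SF-12 models cannot be run as written, because each instrument is scheduled at 0 of 4 assessment times, and three PROMIS scales covering the same domains at 4 of 4 times have no stated analysis. This follows directly from comparing section 6.1 with Table 2 and needs no outside assumption.

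The direction of the 4.5-point rule is less certain. That the plan calls a reduction an improvement is explicit. That this is backwards rests on higher scores meaning better health, which the documents do not state. It is fair to say that the rule appears inverted and that the direction must be given.

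The two n-3 PUFA references are errors against the stated arms, editorial in their effect on the sex analysis. The effect is confined to secondary analyses: the feasibility outcomes, the primary model and the power statements do not change. The correction should be made, but it does not threaten the trial's main aims.

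**What to change.** Before unblinding, amend section 6.1 as follows.

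1. Replace the Brief Pain Inventory by PROMIS Pain Interference 4a, and the SF-12 MCS and PCS by PROMIS Global Mental 2a and Global Physical 2a, with the same mixed model. State for each scale which direction is better.
2. Delete the 4.5-point SF-12 rule. It should not be carried over to the PROMIS scales, because the plan cites it for the SF-12 only. If a responder definition is wanted, give a threshold justified for the chosen scale.
3. Delete both n-3 PUFA references.

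The cost is wording only, since the replacement data are already scheduled at all four times.

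The alternative is to add the Brief Pain Inventory and SF-12 to Table 2. That would also reconcile the passages, but it lengthens the questionnaires and cannot recover baseline values for anyone already enrolled. The direction of the 4.5-point rule and the n-3 PUFA wording would still need correcting.

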6.2 Subject Population(s) for Analysis

We will examine effect of Vitamin D on pain outcomes using an intention to treat paradigm. Participants will be analyzed in the group in which they are randomized.

Safety and Adverse Events

7.1 Definitions

Unanticipated Problems Involving Risk to Subjects or Others

Any incident, experience, or outcome that meets all of the following criteria:

- Unexpected in nature, severity, or frequency (i.e., not described in study-related documents such as the IRB-approved protocol or consent form, the investigators brochure, etc.).
- Related or possibly related to participation in the research (i.e., possibly related means there is a reasonable possibility that the incident experience, or outcome may have been caused by the procedures involved in the research).
- Serious (as defined below) “Serious” is different than “severe” as reported in the CTC criteria that applies a grade to the AE.

Adverse Event

An **adverse event** (AE) is any symptom, sign, illness or experience that develops or worsens in severity during the course of the study. Intercurrent illnesses or injuries should be regarded as adverse events. Abnormal results of diagnostic procedures are considered to be adverse events if the abnormality:

- results in study withdrawal
- is associated with a serious adverse event
- is associated with clinical signs or symptoms
- leads to additional treatment or to further diagnostic tests
- is considered by the investigator to be of clinical significance

Serious Adverse Event

Adverse events are classified as serious or non-serious. A **serious adverse event** is any AE that is:

- fatal
- life-threatening
- requires or prolongs hospital stay
- results in persistent or significant disability or incapacity
- a congenital anomaly or birth defect
- an important medical event

Important medical events are those that may not be immediately life threatening, but are clearly of major clinical significance. They may jeopardize the subject, and may require intervention to prevent one of the other serious outcomes noted above. For example, drug overdose or abuse, a seizure that did not result in in-patient hospitalization, or intensive treatment of bronchospasm in an emergency department would typically be considered serious.

All adverse events that do not meet any of the criteria for serious should be regarded as **non-serious adverse events**.

Adverse Event Reporting Period

The study period during which adverse events must be reported is normally defined as the period from the initiation of any study procedures to the end of the study treatment

follow-up. For this study, the study treatment follow-up is defined as 30 days following the last administration of study treatment.

Preexisting Condition

A preexisting condition is one that is present at the start of the study. A preexisting condition should be recorded as an adverse event if the frequency, intensity, or the character of the condition worsens during the study period.

General Physical Examination Findings

At screening, any clinically significant abnormality should be recorded as a preexisting condition. At the end of the study, any new clinically significant findings/abnormalities that meet the definition of an adverse event must also be recorded and documented as an adverse event.

Post-study Adverse Event

All unresolved adverse events should be followed by the investigator until the events are resolved, the subject is lost to follow-up, or the adverse event is otherwise explained. At the last scheduled survey, the investigator should instruct each subject to report any subsequent event(s) that the subject, or the subject's personal physician, believes might reasonably be related to participation in this study.

Hospitalization, Prolonged Hospitalization or Surgery

Any adverse event that results in hospitalization or prolonged hospitalization should be documented and reported as a serious adverse event unless specifically instructed otherwise in this protocol. Any condition responsible for surgery should be documented as an adverse event if the condition meets the criteria for an adverse event.

Neither the condition, hospitalization, prolonged hospitalization, nor surgery are reported as an adverse event in the following circumstances:

- Hospitalization or prolonged hospitalization for diagnostic or elective surgical procedures for a preexisting condition. Surgery should **not** be reported as an outcome of an adverse event if the purpose of the surgery was elective or diagnostic and the outcome was uneventful.
- Hospitalization or prolonged hospitalization required to allow efficacy measurement for the study.
- Hospitalization or prolonged hospitalization for therapy of the target disease of the study, unless it is a worsening or increase in frequency of hospital admissions as judged by the clinical investigator.

7.2 Recording of Adverse Events

At each contact with the subject, the investigator must seek information on adverse events by specific questioning and, as appropriate, by examination. Information on all adverse events should be recorded immediately in the source document, and also in the appropriate

adverse event module of the case report form (CRF). All clearly related signs, symptoms, and abnormal diagnostic procedures results should be recorded in the source document, though should be grouped under one diagnosis.

All adverse events occurring during the study period must be recorded. The clinical course of each event should be followed until resolution, stabilization, or until it has been determined that the study treatment or participation is not the cause. Serious adverse events that are still ongoing at the end of the study period must be followed up to determine the final outcome. Any serious adverse event that occurs after the study period and is considered to be possibly related to the study treatment or study participation should be recorded and reported immediately.

7.3 Reporting of Serious Adverse Events and Unanticipated Problems

Investigators and the protocol sponsor will conform to the adverse event reporting timelines, formats and requirements of the various entities to which they are responsible, but at a minimum those events that must be reported are those that are:

- related to study participation,
- unexpected, and
- serious or involve risks to subjects or others

(See definitions, section 8.1).

If the report is supplied as a narrative, the minimum necessary information to be provided at the time of the initial report includes:

• Study identifier	• Current status
• Study Center	• The reason why the event is classified as serious
• Subject number	• Investigator assessment of the association between the event and study treatment
• A description of the event	
• Date of onset	

7.3.1 Investigator reporting

7.3.1.1 Unanticipated Problems, Severe Adverse Events

Any study-related unanticipated problem posing risk of harm to subjects or others, and any type of serious adverse event, must be reported to the study data coordinating center by telephone within 24 hours of the event. To report such events, a Serious Adverse Event (SAE) form must be completed by the investigator and faxed/mailed to the data coordinating center within 24 hours. The investigator will keep a copy of this SAE form on file at the study site.

Within the following 48 hours, the investigator must provide further information on the serious adverse event or the unanticipated problem in the form of a written narrative. This should include a copy of the completed Serious Adverse Event form, and any other

diagnostic information that will assist the understanding of the event. Significant new information on ongoing serious adverse events should be provided promptly to the data coordinating center.

7.3.1.2 Other Reportable Events

For clinical drug trials, the following events are also reportable to the UNC IRB:

- Any adverse experience that, even without detailed analysis, represents a serious unexpected adverse event that is rare in the absence of drug exposure (such as agranulocytosis, hepatic necrosis, Stevens-Johnson syndrome).
- Any adverse event that would cause the sponsor to modify the investigators brochure, protocol or informed consent form, or would prompt other action by the IRB to assure protection of human subjects.
- Information that indicates a change to the risks or potential benefits of the research, in terms of severity or frequency. For example:
 - An interim analysis indicates that participants have a lower rate of response to treatment than initially expected.
 - Safety monitoring indicates that a particular side effect is more severe, or more frequent than initially expected.
 - A paper is published from another study that shows that an arm of your research study is of no therapeutic value.
- Change in FDA safety labeling or withdrawal from marketing of a drug, device, or biologic used in a research protocol.
- Breach of confidentiality
- Change to the protocol taken without prior IRB review to eliminate apparent immediate hazard to a research participant.
- Incarceration of a participant when the research was not previously approved under Subpart C and the investigator believes it is in the best interest of the subject to remain on the study.
- Complaint of a participant when the complaint indicates unexpected risks or the complaint cannot be resolved by the research team.
- Protocol violation (meaning an accidental or unintentional deviation from the IRB approved protocol) that in the opinion of the investigator placed one or more participants at increased risk, or affects the rights or welfare of subjects.
- For reportable deaths, the initial submission to the UNC IRB may be made by contacting the IRB Director or Associate Director. The AE/Unanticipated Problem Form is required as a follow up to the initial submission.

7.3.1.3 External Site Reporting

Investigators who are not UNC faculty or affiliated with a UNC research site are responsible for safety reporting to their local IRB. Investigators are responsible for complying with their local IRB's reporting requirements, though must submit the required reports to their IRB no later than 10 working days. Copies of each report and documentation of IRB notification and receipt will be kept in the investigator's study file.

7.4 Unblinding Procedures

Unblinding the group in which the patient is randomized will only occur in exceptional circumstances when the knowledge of treatment is essential for the management of an individual patient. In emergency situations (e.g., anaphylaxis) the principal investigator may contact IDS to have the identity of the patient's treatment drug revealed to help manage the patient more effectively. If this occurs, the unblinding procedure will be documented in the patient's source documents.

